**A randomized controlled trial investigating the pediatric patient experience
of subantimicrobial dose doxycycline for acne treatment**

- Study protocol
- Statistical analysis plan
- Informed consent form

NCT number: NCT05399290

Date: October 8, 2022

Study Protocol

Inclusion criteria

Participants are eligible for inclusion in the study if they: are between ages 13 and 17, diagnosed with moderate to severe acne, did not have other skin conditions on their face, were not previously treated with antibiotics for acne nor received antibiotics for any reason within the last month, did not start a new prescription regimen for their acne within the last three months, did not obtain a positive pregnancy test in the clinic, and had no cognitive impairments. This minimizes confounding factors in treatment response and evaluation of acne (e.g., erythema from other skin conditions). 22 adolescents were identified as eligible and, with their parents, consented to participate in the study during the 11/20/2020 through 09/20/2021 study period. No changes to eligibility were made during the study period.

Randomization and Blinding

Once consent is obtained, eligible sample adolescents are randomized in a non-blinded, parallel fashion and in equal allocation to take either 20 mg or 100 mg doxycycline BID for 12 weeks. Additionally, the same over the counter regimen of Adapalene 0.1% gel and Benzoyl Peroxide 2-5% wash was prescribed.

Patients are randomized by choosing a folded piece of paper from a bag that determined their dose. No blinding to treatment arms occurred to mimic a real world where patients are informed of their dose. This allowed for the determination of patient-perceived effectiveness despite patient awareness of taking a lower dose.

Materials and methods

Participants are emailed a brief Qualtrics survey¹⁸ link on the day of enrollment and every two weeks thereafter to self-report their doxycycline dose and perceived facial acne severity using the validated *Patient-Centered Acne Severity Scale*¹⁹ containing a 10-point visual analog Likert-type scale. Each respondent is also invited to report any medication changes and submit open-ended comments concerning their use of doxycycline or their acne experiences. Those who submit at least three survey responses will be included in the analysis. After 12 weeks of treatment, participants complete a follow-up appointment at three months for clinical evaluation.

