All participants are to be screened, enrolled, and treated through the Messenger Dermatology Clinic. Treatment is initiated at the same visit as enrollment and data collection ends at the three-month appointment. Patients picked up their prescription from the pharmacy of their choosing; the clinic and study personnel do not dispense the medication themselves. The Qualtrics software is programmed with a de-identified study identification number and message encryption.

Statistical Analysis Plan

Data analysis will be performed with *S.P.S.S. Version 28* analytic software using Friedman repeated measures test and Chi square test. For all analytic procedures, a two-tailed coefficient $\alpha < 0.05$ will be observed to indicate statistical significance.

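### The SAP names no analysis that estimates the difference between the two randomised doses in severity score: Friedman has no arm term, and chi-square is tied to no variable, cut-point or time point

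*Combined protocol and SAP*

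**What the plan says.** The Statistical Analysis Plan consists of two sentences. It names the software, states that the data will be analysed "using Friedman repeated measures test and Chi square test", and sets a two-tailed 0.05 level for every procedure. It does not say whether Friedman is run on all patients together or within each arm, which surveys enter it, or what chi-square is applied to. Neither the SAP nor the protocol names a primary outcome, an analysis time point, a between-arm contrast, an effect measure or a confidence interval.

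The design is comparative. Under Randomization and Blinding, patients are "randomized in a non-blinded, parallel fashion and in equal allocation to take either 20 mg or 100 mg doxycycline BID for 12 weeks", and for both arms "the same over the counter regimen of Adapalene 0.1% gel and Benzoyl Peroxide 2-5% wash was prescribed". The reason given for leaving patients unblinded is: "This allowed for the determination of patient-perceived effectiveness despite patient awareness of taking a lower dose".

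Under Materials and methods, patients are surveyed "on the day of enrollment and every two weeks thereafter to self-report their doxycycline dose and perceived facial acne severity", on an instrument "containing a 10-point visual analog Likert-type scale". The same section sets the analysis set and the end of follow-up: "Those who submit at least three survey responses will be included in the analysis"; "data collection ends at the three-month appointment".

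**The concern.** The only repeated-measures test in the plan asks whether scores change across visits within patients. That is not the question the randomisation was set up to answer.

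- Run on all patients, Friedman ignores dose.
- Run separately in each arm, it gives two p-values, and comparing them is not a test of the dose difference.
- Both arms use the same topical regimen, so a fall within one arm cannot by itself be put down to the doxycycline dose.
- Chi-square is able to compare arms, but the plan does not say on what, and a p-value from a dichotomised score is not a difference in points.

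At stake is the trial's main product. A team that followed the plan exactly could report that severity fell, yet could not say how far the two doses differ or how uncertain that difference is. A description of change in the low-dose arm would fit the title, but it would make no use of the randomised comparison.

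**Working it through.** **Inputs from the documents.** Two arms, equal allocation; 22 consented, so 11 per arm if the split is exact (arm counts are not stated); a 10-point score at enrolment and every two weeks, which is seven surveys (weeks 0, 2, 4, 6, 8, 10, 12) if the schedule runs to week 12; an analysis set of patients with at least three surveys; two-sided 0.05. There is no sample-size calculation, mean, SD, expected fall or response rate, so the plan has no figure to reproduce.

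**Assumed, for illustration only.** Integer scores 1 to 10, baseline mean 6.5, between-patient SD 1.5, within-patient SD 1.2 (1.6 in brackets), linear falls, surveys missing independently at random, 4000 simulated trials per setting.

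**Step 1: Friedman on all patients.** With n patients, k visits and R_j the sum over patients of the within-patient ranks at visit j, the statistic without ties is

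Q = 12 / [n k (k+1)] × Σ R_j² − 3 n (k+1).

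Only within-patient ranks enter. A constant added to all of a patient's scores changes no rank, and arm membership appears nowhere. In a simulated data set, adding 100 points to every score in one arm left Q at 26.66 (p = 0.00017) both times. This holds whatever the SDs.

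A separate simulation (between-patient SD 1, within-patient SD 1.5) shows the consequence. With trends of 0.3 points per visit in opposite directions, pooled Friedman rejected in 2% of trials, and a between-arm test on change from baseline in 95%. With an equal fall of 0.3 per visit in both arms, pooled Friedman rejected in 93%.

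**Step 2: Friedman per arm, p-values compared (the SAP does not say this is intended).** If the arms are identical and each reaches significance with probability p, they disagree with probability 2p(1−p), which peaks at 0.5 when p = 0.5. Simulated disagreement between identical arms:

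| Fall in both arms | 0 | 1 | 1.25 | 1.5 | 2 | 2.5 | 3 |
|---|---|---|---|---|---|---|---|
| SD 1.2 | 8.4% | 42.2% | 48.4% | 44.7% | 17.2% | 2.2% | 0.1% |
| SD 1.6 | 8.4% | 27.1% | 37.4% | 47.0% | 46.3% | 24.6% | 7.1% |

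Between-arm ANCOVA, checked with equal falls of 2, rejected in 4.3% to 5.5% of trials across both SDs and all response rates.

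**Step 3: patients used, of 22.** Friedman on all seven visits needs every score; ANCOVA needs enrolment and week 12.

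| Response per survey | Seven-visit Friedman | ANCOVA |
|---|---|---|
| 90% | 22 × 0.9^7 = 10.5 | 22 × 0.9² = 17.8 |
| 80% | 22 × 0.8^7 = 4.6 | 22 × 0.8² = 14.1 |

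**Step 4: what a between-arm analysis would deliver.** Falls of 2 versus 4 points; chi-square is on a fall of 3 or more in the same patients.

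| Response | ANCOVA power | ANCOVA on ranks | Chi-square, uncorrected | Chi-square, corrected | ANCOVA 95% CI half-width |
|---|---|---|---|---|---|
| 100% | 78.5% (57.7%) | 76.7% (56.7%) | 49.6% (32.7%) | 32.4% (18.4%) | 1.29 (1.58) |
| 90% | 66.1% (47.5%) | 64.6% (46.7%) | 43.5% (27.6%) | 23.1% (12.6%) | 1.49 (1.82) |
| 80% | 51.1% (36.4%) | 49.5% (36.1%) | 34.9% (24.2%) | 14.2% (9.4%) | 1.79 (2.18) |

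Hand check of the complete-data half-width at SD 1.2, ignoring rounding and clipping: variance 1.5² + 1.2² = 3.69; correlation 2.25/3.69 = 0.610; residual SD √[3.69 × (1 − 0.610²)] = 1.52; half-width 2.093 × 1.52 × √(2/11) = 1.36. The simulated 1.29 is a little smaller, as expected because clipping at 1 compresses the scores; it also makes the mean estimated difference 1.73 to 1.82 rather than 2.

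For falls of 2 versus 3, ANCOVA power is 27.7% (19.1%), 24.2% (15.6%) and 17.6% (12.4%) at the three response rates.

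**Step 5: timing.** Consent ran to 09/20/2021. Adding 84 days gives 12/13/2021, which is 299 days before the document date of October 8, 2022.

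**The case against.** **The purpose may be descriptive.** The title speaks of patient experience of the low dose, and no dose-comparison hypothesis is stated. This is a fair reading and it limits the point: the between-dose difference is inferred as the natural target. But the title also calls this a randomised controlled trial, and the stated reason for not blinding concerns perceived effectiveness in patients who know they take the lower dose. A purely within-arm report leaves the randomisation unused.

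**The trial is small and the data are in.** Both are true. Low precision is a reason to show an interval, not to omit the estimate, and late specification is handled by labelling.

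**ANCOVA also departs from the three-survey rule.** This stands as a cost: a patient with five surveys but no week-12 score is dropped. A t-test on each patient's fitted slope keeps nearly everyone. With linear falls of 2 versus 4 and SD 1.2, it gave 84%, 78% and 67% power at 100%, 90% and 80% response, against 76%, 65% and 50% for ANCOVA in the same runs. That lead depends on linearity. At 90% response and SD 1.2, slope led 80% to 69% with linear falls but trailed 61% to 66% when improvement came early and then levelled off. A slope also answers a different question from the week-12 score. So ANCOVA is a sound choice, not the only one.

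**The mixed model was checked only in part.** This is also fair: only a random intercept-and-slope model was run, with 388 to 586 replicates per setting, and its power was not assessed.

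**Every simulation input is assumed.** Yes, but the central point rests on how the two tests work.

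**Conclusion.** The point holds and should be fixed before results are reported. Followed as written, the plan yields no estimate and no confidence interval for 20 mg versus 100 mg on the 10-point severity score, the only outcome for which the protocol gives a scale. The structural part needs no numerical assumption: Friedman cannot see the arm, and chi-square is unspecified and gives no difference in points.

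The sizes are conditional on the assumed SDs, falls and independent missingness. Per-arm Friedman results from identical arms could disagree in about 0% to 48% of trials. A seven-visit Friedman would use about 10.5 of 22 patients at 90% response. For a 2-point difference in fall, a chi-square on the dichotomised score has clearly less power than ANCOVA (50% against 78% at SD 1.2 with complete data, uncorrected).

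**What to change.** Rewrite the SAP as follows.

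- **Between-arm analysis:** ANCOVA of the week-12 severity score with arm as factor and enrolment score as covariate. Report the adjusted difference (20 mg minus 100 mg) with its 95% CI at two-sided 0.05, and the number per arm with both scores.
- **If a rank method is preferred:** use ANCOVA on ranks for the test, and still report the adjusted difference and CI, because ranks give no difference in points.
- **Friedman:** keep it as a descriptive within-arm summary, name the visits it uses, and do not use it to compare doses.
- **Chi-square:** state the variable, cut-point and time point for each use.
- **Mixed model of all post-baseline scores:** supportive only. With random intercept and slope at n = 22, its week-12 size was 3% to 5%, but 20% to 51% of fits lay on the variance boundary and 2% to 5% did not converge. Report any such fit. Satterthwaite and Kenward-Roger degrees of freedom were not checked.
- **Label** the new analysis as specified after data collection, whether or not results have been seen.

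The change costs SAP wording and a few lines of code, with no new data. Its limits should be stated openly:

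- ANCOVA drops about 4 of 22 patients at an assumed 90% response and about 8 at 80%.
- It treats a 10-point score as roughly continuous; the rank version avoids this at almost the same power.
- For a 1-point difference in fall, power is only about 12% to 28%.

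The gain is an honest estimate with its interval, not a definitive dose comparison.

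### The analysis set admits patients with missed surveys, but the only repeated-measures test named (Friedman) needs a score at every time point entered and does not compare the two doses

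*Combined protocol and SAP*

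**What the plan says.** Under Materials and methods, participants receive a survey "link on the day of enrollment and every two weeks thereafter", each containing a 10-point rating of facial acne severity. The rule for the analysis set follows: "Those who submit at least three survey responses will be included in the analysis". It does not say which weeks must be covered, or that baseline or the last survey must be among them.

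The number of surveys is not stated. Treatment lasts 12 weeks, "data collection ends at the three-month appointment", and that visit is described as one for clinical evaluation. The schedule therefore implies seven surveys (weeks 0, 2, 4, 6, 8, 10, 12), or six if none is sent at week 12.

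Patients are "randomized in a non-blinded, parallel fashion and in equal allocation" to one of two doses, and "22 adolescents were identified as eligible" and consented (Inclusion criteria).

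The Statistical Analysis Plan is two sentences long. It names the software, the two methods ("using Friedman repeated measures test and Chi square test") and a two-tailed 0.05 criterion. It does not say which variable goes with which test, which surveys are compared, or what happens when one is missed.

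**The concern.** Friedman's test ranks each patient's scores across a fixed set of time points, so a patient with a gap at any of them cannot be ranked unless the gap is filled or the scores are realigned. The inclusion rule expressly admits patients with gaps. The two provisions fit together only after a further decision, and the plan does not make one. Two analysts following it could test different patients.

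If the scheduled surveys are entered as they stand, the tested set can be smaller than the stated analysis set and is selected on something that happens after randomization. In an unblinded trial, returning surveys may be related to dose or to perceived benefit. With 22 patients in two arms, losing a few matters.

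The test also answers a different question from the one the design poses. It asks whether scores change over time within patients. Whether it is run on everyone or separately in each arm, it does not test whether the change differs between doses.

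**Working it through.** The plan gives no sample-size or response-rate figure, so there is nothing of its own to reproduce. The check asks how far the inclusion rule and the test can diverge.

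**Inputs from the documents:** 22 patients; inclusion at three or more surveys; seven scheduled surveys (six as the alternative).

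**Assumptions:** response per survey p = 0.90; within-patient correlation of response (ICC) 0, 0.3 or 0.6; every week equally likely to be missed. None of these is in the documents.

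**Patterns.** With seven surveys, the response patterns that qualify number C(7,3) + C(7,4) + C(7,5) + C(7,6) + C(7,7) = 35 + 35 + 21 + 7 + 1 = 99, of which one is complete. With six surveys it is one of 20 + 15 + 6 + 1 = 42.

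**Formula.** Loss among included = 1 − P(all needed surveys answered) / P(three or more answered). With ICC = 0 the counts are binomial. Otherwise they are beta-binomial with a = p(1 − ICC)/ICC and b = (1 − p)(1 − ICC)/ICC, so that P(m given weeks all answered) is the product of (a + j)/(a + b + j) over j = 0 to m − 1.

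- ICC 0: P(all 7) = 0.9^7 = 0.478 and P(≥3) = 1.000, so the loss is 1 − 0.478/1.000 = 52%.
- ICC 0.6: a = 0.9 × 0.4/0.6 = 0.600 and b = 0.1 × 0.4/0.6 = 0.067. P(all 7) = 0.798 and P(≥3) = 0.931, so the loss is 1 − 0.798/0.931 = 14%.

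Seven surveys, p = 0.90 (patients = 22 × difference in probabilities):

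| ICC | P(≥3) | P(all 7) | Loss, all seven | P(3 fixed weeks) | Loss, three fixed weeks |
|---|---|---|---|---|---|
| 0 | 1.000 | 0.478 | 52% (11.5 patients) | 0.729 | 27% (6.0) |
| 0.3 | 0.969 | 0.686 | 29% (6.2) | 0.792 | 18% (3.9) |
| 0.6 | 0.931 | 0.798 | 14% (2.9) | 0.842 | 10% (2.0) |

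With six surveys the losses for ICC 0, 0.3 and 0.6 are 47%, 26% and 13% (all six) and 27%, 17% and 9% (three fixed weeks).

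**Other response rates** (seven surveys, ICC 0.6 to 0): at p = 0.80, 27% to 79% for all seven and 18% to 49% for three weeks; at p = 0.95, 7% to 30% and 5% to 14%.

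**Drop-off instead of scattered misses.** Suppose everyone answers at week 0, a constant fraction q continues from each survey to the next, and the average response is still 90%. Solving (1 + q + … + q^6)/7 = 0.90 gives q = 0.9647. Then P(≥3) = q^2 = 0.9306 and P(all 7) = q^6 = 0.8058, so the loss is 1 − 0.8058/0.9306 = 13%, about 2.7 patients. For weeks 0, 2 and 4 the loss is nil, because being included then means having answered exactly those weeks. Any set of weeks that includes week 12 loses the same 13%.

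**The inclusion rule itself.** Of 22, it excludes 22 × (1 − P(≥3)) = 0.0, 0.7 and 1.5 patients for ICC 0, 0.3 and 0.6 (seven surveys), and about 1.5 under drop-off.

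**The case against.** The strongest reply is that this is a silence in a very short plan, and that the size of the harm is assumed throughout. No response rate is given; if everyone answered every survey, nothing is lost. The upper figures of 52% and 47% require a patient's misses to be unrelated to one another, which is unlikely. Drop-off, a plausible pattern, puts the all-survey loss slightly below the bottom of the range and removes the loss on the first three weeks altogether. All of that stands, and it is why the figures can only be illustrations. It does not remove the mismatch: a threshold of three shows that partial response was expected.

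A reader might infer that the threshold means each patient's first three responses are the repeated measures, so that different weeks are ranked as if they were the same. The documents do not support this. Three is stated as a condition for inclusion, not as the set of columns in the test, and the described schedule makes the calendar surveys the more natural choice. Nor are dropping and realigning the only options: filling in missed scores is equally open.

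That the weeks are unrestricted, and that Friedman is meant for the severity score, are both inferences from what the plan leaves unsaid, though fair ones. Patients with gaps may still contribute to the chi-square test and to the open comments.

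Finally, a model with seven separate visits in two arms has 14 means to estimate from 22 patients. That objection to an elaborate model is sound, and the proposed change allows for it.

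**Conclusion.** The concern holds as a mismatch between the analysis set and the only repeated-measures test named. If the scheduled surveys are entered without filling in, included patients with a gap leave the test, and the test does not compare the doses in any case.

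The size cannot be established from the documents. At an assumed 90% response over seven surveys, with weeks equally likely to be missed and ICC from 0.6 to 0, the loss is 14% to 52% of included patients for an all-survey test and 10% to 27% for three fixed weeks. Under drop-off with the same average it is about 13%, and nil for weeks 0, 2 and 4. It would be wrong to conclude that half the patients were lost, or that any particular handling of gaps was used; a reader cannot tell from the plan. The change should be made, but confidence in the practical size of the effect is only moderate.

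**What to change.** Analyse the severity score with a simple mixed model that uses every submitted survey: arm, visit and arm-by-visit, a random intercept per patient, and small-sample degrees of freedom. Keep the baseline score as one of the repeated outcomes, so that a patient who missed week 0 still contributes. To limit parameters, visit may be entered as a linear time term, which reduces the mean structure from 14 terms to four (intercept, arm, time, arm-by-time). The arm-by-visit or arm-by-time term supplies the dose comparison. Using every survey means letting patients with one or two surveys into this model.

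If Friedman is kept, name the calendar weeks it compares, label it complete-case and within-patient only, and report the number contributing per arm.

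In either case, state how many surveys are scheduled, and report surveys received per visit and arm and the number per arm excluded by the three-survey rule. That rule is itself a selection on completion, so repairing only the Friedman step would leave it in place.

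The cost is SAP wording and modest programming, with no new data. The model adds assumptions for a 10-point score in 22 patients and treats missed surveys as ignorable; patients with no survey still cannot be analysed. On timing, patients "consented to participate in the study during the 11/20/2020 through 09/20/2021 study period", and the document is dated October 8, 2022. That is 383 days after the period's last day. Even a patient enrolled on that day would have finished 12 weeks (84 days) on December 13, 2021, 299 days before the document date. The real counts were therefore probably available and should replace the assumed rates. If the data had already been seen, the change must be labelled post hoc.

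### The SAP names no suitable between-arm test for the 10-point severity score: Friedman cannot compare the doses, and chi-square ignores the score's ordering and is very sparse at 22 patients

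*Combined protocol and SAP*

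**What the plan says.** The analysis section is two sentences long. The first names the software and the methods, "Friedman repeated measures test and Chi square test". The second sets the threshold: "two-tailed coefficient $\alpha < 0.05$ will be observed to indicate statistical significance". Neither test is assigned to a variable, a time point or a comparison, and no table shape, continuity correction or exact version is given.

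The rest comes from the Study Protocol:

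- **Number of patients** (Inclusion criteria): "22 adolescents were identified as eligible and, with their parents, consented to participate in the study".
- **Allocation** (Randomization and Blinding): "in equal allocation to take either 20 mg or 100 mg doxycycline BID for 12 weeks", which is about 11 per arm.
- **Outcome** (Materials and methods): self-rated facial acne severity on a 10-point scale, collected on the enrollment day and then fortnightly. It is the only outcome described numerically; no yes/no endpoint is defined.
- **Analysis set** (Materials and methods): "Those who submit at least three survey responses will be included in the analysis". The analysed number can therefore be below 22.

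The documents contain no sample-size or power calculation.

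**The concern.** The trial randomizes patients to one of two doses, so its central comparison is between arms. A reader who takes the SAP literally has two ways to make that comparison on the severity score, and neither is adequate.

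One is to run Friedman's test separately in each arm and compare the two p-values. That shows whether scores changed over time within an arm. It does not test whether the arms differ, because one significant and one non-significant within-arm result can arise with no difference between doses.

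The other is to cross-tabulate score category by arm and apply chi-square. That test treats a move from 3 to 4 no differently from a move from 3 to 9. With so few patients per cell it rarely rejects. In a trial of a lower against a higher dose, a non-significant result from an insensitive test could then be read as evidence that the doses perform alike.

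**Working it through.** The plan has no power figure to reproduce, so the check asks what each named test can do with the design as described.

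**1. Friedman.** The test ranks repeated measurements within each block. Here the block is the patient and the repeated factor is the survey date. Dose is constant within a patient, so it drops out of the within-block ranks. The statistic carries no arm comparison.

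**2. Sparseness of chi-square on the score.**

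- An arm-by-score table has 2 x 10 = 20 cells. With 22 patients spread evenly, the expected count is 22/20 = 1.1 per cell. If only five categories are used it is 22/10 = 2.2.
- With all ten categories occupied, df = (2 - 1) x (10 - 1) = 9 and the 5% critical value is 16.92.
- The largest value the statistic can take in a two-row table is N = 22, reached only when the arms share no category. Rejection needs 16.92/22 = 77% of that maximum.
- With seven categories occupied, df = 6, the critical value is 12.59, and 12.59/22 = 57% of the maximum is needed.

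**3. Size and power by simulation.** From the documents: two-sided 0.05, 11 per arm, scores 1 to 10, baseline available. Assumed, because the documents give none of them: normal scores rounded and limited to 1-10, SD 2 (also 1.5), baseline-to-final correlation 0.5, and differences of 0 to 3 points. There were 3,000 to 4,000 runs per setting, and up to 40,000 for the size of chi-square. Ranges cover independent runs.

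| Per arm | SD | True difference | Chi-square on categories | Rank-sum | ANCOVA |
|---|---|---|---|---|---|
| 11 | 2 | 0 (size) | 1-2% | 4-5% | 5% |
| 11 | 2 | 1 point | 3% | 17% | 21-22% |
| 11 | 2 | 2 points | 8-10% | 54-57% | 67-69% |
| 11 | 2 | 3 points | 23-28% | 89% | 96% |
| 11 | 1.5 | 2 points | 21-22% | 80% | 90% |
| 11 | 1.5 | 3 points | 54-59% | 99% | over 99% |
| 9 | 2 | 2 points | 5-6% | 46-47% | 57-60% |

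**4. Analytic cross-check (2 points, SD 2, 11 per arm).**

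- Unadjusted t-test: noncentrality = 2 / (2 x √(2/11)) = 2.35 on 20 df, power 61% (simulated 60%).
- ANCOVA: residual SD = 2 x √(1 - 0.5²) = 1.73; noncentrality = 2 / (1.73 x √(2/11)) = 2.71 on 19 df, power 73%. The simulated 67-69% is lower because of rounding, truncation and chance baseline imbalance.
- Rank-sum on change from baseline: SD of change = 2 x √(2 x (1 - 0.5)) = 2, the same as the raw score, so power is about that of the rank-sum row (simulated 55%).

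**5. Yes/no tables, for completeness.** Enumerating all 2x2 tables and maximising over a common event rate, the largest true size of the uncorrected chi-square is 5.28% at 11/11, 6.35% at 11/10, 4.22% at 10/10 and 7.7% at 8/8. With Yates' correction it is at most 2.1% in every split checked. At 11/11 with event rates of 20% v 70%, power is 70% for uncorrected chi-square, 64% for Boschloo's exact test and 52% for Fisher's.

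**The case against.** The strongest reply is that the SAP never says chi-square will be run on the ten score categories. The repeated score pairs naturally with the repeated-measures test, and chi-square may be meant for something else. That is correct, and it makes the power figures conditional. It does not rescue the plan: if chi-square is not for the score, then no between-arm test of the score is named at all.

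A second reply is that chi-square is not powerless for every effect. That also stands. For a 3-point difference it reaches 23-28% at SD 2 and 54-59% at SD 1.5, so it would be wrong to say that a real difference would almost always be missed. It remains far below the alternatives in every setting.

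A reader might also infer that chi-square fails its 5% level in any trial of this size and must be replaced by an exact test. The documents do not support that. They define no yes/no endpoint and do not say whether a correction would be used. At the planned 11/11 the excess is 0.3 percentage points at worst, and at 10/10 there is none. The larger excesses need uneven or depleted splits, which the paper draw and the three-survey rule permit but which are not reported. An exact test costs power (70% down to 64% or 52% in the example above), so the choice is a trade-off.

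**Conclusion.** The point holds for the severity score. Neither named test is a suitable between-arm comparison of the trial's only numerical outcome. That rests on the SAP's wording and on how the two tests work, not on any assumed number.

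The size of the loss does rest on assumptions. With 11 per arm, SD 2 and baseline correlation 0.5, chi-square on the categories would give up roughly 45 points of power against a rank-sum test and nearly 60 against ANCOVA for a 2-point difference. The ordering of the three tests is the same at SD 1.5 and at 9 per arm.

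The point does not extend to a general loss of the 5% level, nor to a claim that the score was in fact to be analysed by chi-square.

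**What to change.** Add to the SAP wording such as:

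> *The severity score at a named survey is compared between randomized arms by ANCOVA with the enrollment-day score as covariate. A rank-sum test on change from baseline is the sensitivity analysis. The arms are not compared by chi-square on score categories or by separate Friedman tests within each arm. Friedman's test describes change over time only.*

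The survey must be specified; the 12-week one is the natural choice. The SAP should also say which variable, if any, chi-square is for. If that variable is yes/no, an exact test may be chosen with its power cost acknowledged, but this is not a required correction.

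The cost is a few sentences and a few lines of code. No new data are needed, because the baseline score is already collected. The real cost is timing. The document is dated October 8, 2022, and the stated study period ended on 09/20/2021. A patient who entered on that last day would have completed 12 weeks in December 2021. A change made now would follow data collection and should be disclosed as post hoc.

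### The SAP tests everything at an unadjusted 0.05 and names no primary outcome, time point or between-arm contrast, so the overall false-positive rate is not controlled at 5%

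*Combined protocol and SAP*

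**What the plan says.** The section headed Statistical Analysis Plan says the data will be analysed "using Friedman repeated measures test and Chi square test". It then sets the threshold in a sentence that opens "For all analytic procedures, a two-tailed coefficient" and takes alpha below 0.05 as the mark of significance. It does not link either test to an outcome, a time point or a contrast. It gives no number of tests, no testing order and no adjustment.

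The Study Protocol describes the design to which this applies:

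- Randomization and Blinding: participants are allocated "in equal allocation to take either 20 mg or 100 mg doxycycline BID for 12 weeks", and both arms also use the same adapalene and benzoyl peroxide regimen. On the lack of blinding it says "This allowed for the determination of patient-perceived effectiveness despite patient awareness of taking a lower dose", which is the nearest thing to a stated objective.
- Materials and methods: participants report "perceived facial acne severity using the validated" Patient-Centered Acne Severity Scale, "on the day of enrollment and every two weeks thereafter". After 12 weeks, "participants complete a follow-up appointment at three months for clinical evaluation", with no measure defined for that evaluation. Anyone with three or more survey responses enters the analysis.

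No outcome is called primary or secondary anywhere in the document.

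**The concern.** A 0.05 threshold limits the error of one test. When the same threshold is given to every test and none is designated as the answer, the chance that at least one is significant by luck is no longer held at 5%. With 22 unblinded participants and a self-reported scale, one isolated small p-value could be presented as the trial's result when it is only one of several tests of equal standing.

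The named procedures also leave the dose question without a clear test. The Friedman test asks whether scores differ across repeated surveys within the same people. It does not compare two independent groups. The chi-square test could compare the arms, but the SAP does not say on what variable or when. A reader could then be shown a significant Friedman result in one arm and not in the other, and take that as a dose effect.

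**Working it through.** **Is there a figure to reproduce?** No. The document gives no sample-size calculation, power, overall error rate or count of tests. The stated 0.05 is the error of a single test: 1 − 0.95^1 = 5%.

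**Inputs from the document.** Threshold 0.05, two-tailed, for each procedure; two named procedures; two arms; 22 participants, so about 11 per arm under equal allocation. Surveys at day 0 and every two weeks to week 12 give 1 + 12/2 = 7, of which 6 are post-baseline.

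**Assumed.** The number of tests k and the correlation between them.

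**Independent tests, all null hypotheses true.** The chance of at least one false positive is 1 − 0.95^k.

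| k | Illustration | Result |
|---|---|---|
| 1 | one named primary test | 5.0% |
| 2 | one test per named procedure, or one Friedman test per arm | 9.75% |
| 3 | any three tests | 14.3% |
| 8 | two Friedman tests plus six chi-square tests | 33.7% |

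**Two correlated tests.** Simulated normal test statistics give 9.1% at correlation 0.5, 7.0% at 0.9 and about 5.6% at 0.99. The excess disappears only when the two tests are almost the same test.

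**Small-sample check of the k = 8 illustration.** The simulation used 11 per arm and seven surveys, with no time or arm effect. Scores were rounded to a 1 to 10 range, with assumed SD 2, a cut at 5.5 for the chi-square tests, and within-person correlation 0 to 0.8.

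- Two Friedman tests, one per arm: 8.1% to 9.1%.
- All eight tests, chi-square without continuity correction: 26.8% to 31.6%.
- All eight tests, with continuity correction (conservative at this size): 14.5% to 17.1%.

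The same eight tests therefore span about 15% to 34%, depending on correlation and on a correction the SAP does not mention.

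**What the two-arm Friedman case looks like.** If neither arm changes, the chance that exactly one arm is significant is 2 × 0.05 × 0.95 = 9.5%, and that both are is 0.05 × 0.05 = 0.25%; together 9.75%. Nearly all of the error is the one-arm-only pattern, the one most easily misread as a dose difference. If both arms truly change by the same amount and each test has power p, the one-arm-only pattern has probability 2p(1 − p), which exceeds 9.5% for every p between 0.05 and 0.95. There each significant result is a true rejection, but the contrast between the arms is still not evidence about dose.

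**The case against.** The strongest reply is that the SAP may plan very few outcome tests. One Friedman test plus a chi-square test used only to compare baseline characteristics would fit its wording and leave a single outcome test at 5%. That reading is possible, and it is why no overall rate can be asserted. But the SAP does not commit to it, and under it the one outcome test would not compare the arms.

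Three stronger readings are tempting, and the document does not support them.

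- A reader might infer that any one significant result makes the trial positive. The SAP says only what will be called statistically significant for each procedure; it has no success criterion.
- A reader might infer that the error rate is about a third, or well above 5% whatever is done. That needs an assumed family of tests. Nothing says the 10-point scale will be dichotomised, or tested at each survey.
- A reader might count the seven surveys as seven tests. A Friedman test is one omnibus test across all of them, and no pairwise follow-up is planned.

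It is also fair to say that one named scale and the stated interest in patient-perceived effectiveness show what the main measure is in practice. That stands, but it fixes no time point, summary or contrast. Finally, since both arms are treated, the within-arm null may be false, so a within-arm rejection need not be a false positive. That is correct, and it adds to the reasons for naming a between-arm comparison.

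**Conclusion.** The point holds in a limited form. The plan does not control the overall false-positive rate at 5%, because it applies 0.05 to every procedure and designates no primary outcome, time point or contrast. The actual rate cannot be determined from the document. With two independent tests it is 9.75%, falling to about 7% if they are highly correlated; these rates assume that all null hypotheses are true. The range of about 15% to 34% belongs to one assumed set of eight tests and should be quoted only as an illustration.

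Independently of the error rate, a significant Friedman result does not answer the dose question. The plan should be changed, but the defect is an absent designation and a missing between-arm test, not a stated rule that one significant result is enough.

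**What to change.** Add to the Statistical Analysis Plan text to this effect:

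- The single primary analysis is the difference between randomized arms in the Patient-Centered Acne Severity Scale score at week 12, adjusted for the day-0 score, tested once at two-sided 0.05 and reported with its confidence interval. Use ANCOVA, or a repeated-measures model fitted to all available surveys.
- State how participants without a day-0 or week-12 score are handled. The three-response rule admits such people. The repeated-measures model lets those missing week 12 still contribute; ANCOVA on observed scores would drop them.
- All Friedman, chi-square and by-visit results are exploratory, reported with estimates and without claims of significance.
- Date the designation and state whether outcome data had been seen. The document is dated October 8, 2022, and its stated study period ended on 09/20/2021; even a participant enrolled on that last day would have finished 12 weeks in December 2021. If outcomes had been seen, the result should be labelled post hoc and exploratory, because naming a primary test at that stage cannot restore a prespecified 5%.

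The cost is one analysis beyond the two procedures now named, plus fewer results that may be called significant. No new data are needed. Splitting alpha by Bonferroni would also control the error, at 0.05/2 = 0.025 per test for two tests or 0.05/8 = 0.00625 for eight, but with 22 participants the loss of power would be large, so one named contrast is the more workable choice.
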